### 3.2 Non-Safety Analysis Sets

The cases below shall be included in Non-safety analysis set in the following order:

- (1) Subjects who have consented prior to the contract
- (2) Subjects who have been administered prior to the contract\*
- (3) Subjects who violated inclusion/exclusion criteria (see section 2.3)
- (4) Subjects who were prescribed for other indications except indications in the local product document.

[Target Indication]

- Fluarix Tetra is indicated for active immunisation of adults and children from 6 months of age for the prevention of influenza disease caused by the influenza A virus subtypes and the influenza B virus types contained in the vaccine.

- (5) Subjects who violate the dosage

[Dosage]

- Children from 6 months and older receive 0.5 ml dose by intramuscular injection and is revaccination each year.
- For children aged < 9 years, who have not previously been vaccinated against influenza, a second dose should be given after an interval of at least 4 weeks.

- (6) Subjects of contraindications

[Contraindication]

	CONFIDENTIAL : THIS DOCUMENT AND INFORMATION CONTAINED HEREIN IS PROPRIETARY TO COMPANY AND IS NOT TO BE DISCLOSED WITHOUT THE WRITTEN PERMISSION OF COMPANY.	Last Update Date 10-SEP-2021
STATISTICAL ANALYSIS PLAN(V5.0)		

- History of hypersensitivity to the active substances or to any of the excipients or to any component that may be present as traces such as eggs (ovalbumin, chicken proteins), formaldehyde, gentamicin sulphate and sodium deoxycholate
- Immunisation should be postponed in patients with febrile illness or acute infection.
- History of hypersensitivity reaction to Influenza vaccine
- History of Guillain-Barre syndrome or other nervous abnormalities to Influenza vaccine within 6 weeks post-vaccination

\* But subjects not administered the Fluarix Tetra this season shall be included from safety analysis set. In addition, subjects under age 9 years who participating in the drug use investigation with a second dose of Fluarix Tetra shall be included from safety analysis set.

### 3.3 Efficacy Analysis Sets

Not Applicable

## 4. Endpoint

### 4.1 Safety Endpoint

- Occurrence of expected and unexpected AEs during the 21 days (Day 0 to Day 20) follow-up period after vaccination
- Occurrence of SAEs starting from the date of vaccination in the drug use investigation up to 21 days (Day 0 to Day 20) after vaccination of the subject in the drug use investigation

## 5. Assessment Criteria

### 5.1 Safety Assessment Criteria

All AEs including ADRs and SAEs reported during the 21 days (Day 0 to Day 20) follow-up period after administration.

	CONFIDENTIAL : THIS DOCUMENT AND INFORMATION CONTAINED HEREIN IS PROPRIETARY TO COMPANY AND IS NOT TO BE DISCLOSED WITHOUT THE WRITTEN PERMISSION OF COMPANY.	Last Update Date 10-SEP-2021
STATISTICAL ANALYSIS PLAN(V5.0)		

## 6. Statistical Analysis

- Each statistical analysis will be carried out with SAS Software version 9.4 or more recent version.
- Data including sign of inequality such as “ $\geq 20$ ”, “ $> 20$ ” will be excluded from analysis.
- All test statistics will be the results of two-sided tests with the statistical significant level 0.05.
- The followings will be included in the final report only.
  - Analysis by type of general medical history/physical examination (Past/Current)
  - Analysis by type of vaccination history
  - Analysis by type of concomitant medications
  - Analysis by type of concomitant vaccination
  - Logistic regression analysis of occurrence of AE
  - Pregnancy report analysis, if the data is collected
  - Preferred terms of Serious AE/Serious ADR, unexpected AE/ADR according to the proportion of AE
  - Other analyses (see section 6.3.3)
- Each study group (3 years old and above, and 6-35 months old) will be analyzed separately.

### 6.1 Composition of Subjects

- Number of enrollment subjects
- Number of subjects for safety analysis set
- Number of subjects excluded from the safety analysis set

### 6.2 Subject characteristics

Data for the subject characteristics is demonstrated by descriptive statistics for safety analysis set.

In the descriptive statistics, number of subjects (N), mean, standard deviation, median, minimum and maximum will be calculated for continuous variables, and frequency and percentage for categorical variables.

The following subject characteristics will be reported:

< Subject baseline Information >

- Gender, Age, Height, Weight, BMI, Ethnicity, General medical history/physical examination

GlaxoSmithKline  
 Protocol No. 204687[EPI-FLU-050 VS KR PMS]

	CONFIDENTIAL : THIS DOCUMENT AND INFORMATION CONTAINED HEREIN IS PROPRIETARY TO COMPANY AND IS NOT TO BE DISCLOSED WITHOUT THE WRITTEN PERMISSION OF COMPANY.	Last Update Date 10-SEP-2021
STATISTICAL ANALYSIS PLAN(V5.0)		

(Past/Current)

< Study Medication Information >

- Vaccination history (influenza vaccination, any non-influenza vaccination), Pre-vaccination body temperature, Dose of Fluarix Tetra administration(All subjects, Subjects under age 9 years\*), Concomitant medication, Concomitant vaccination, Route of concomitant vaccination

< Special Subject Information >

- Pediatric group ( $\geq 3$  years and  $< 19$  years)\*, Elderly group ( $\geq 65$  years)\*, Pregnancy\*, Liver disorder, Kidney disorder

\* Not applicable for study group aged 6-35 months

### 6.3 Safety Analyses

Safety analysis on safety parameter will be done on safety analysis set.

In the safety analysis set, the number of subjects to whom AE occurred and the number of AEs will be calculated. Also, the incidence proportion of AEs and its 95% confidence interval will be estimated.

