4.2. Inclusion criteria for enrolment

All subjects must satisfy the following criteria at drug use investigation entry:

- Male or female subjects who were vaccinated with *Fluarix Tetra* or eligible to receive *Fluarix Tetra* according to the locally approved PI.

Note: According to current approved PI, the subjects below are included.

Subjects	1 st dose	Follow-up contact after 21 days	2 nd dose	Follow-up contact after 21 days
Primed	●	●		
Unprimed ¹	●	●	●	●
Unprimed ²	●	●		
Unprimed with history of Fluarix Tetra ³			●	●

- Primed: adults and previously vaccinated children aged ≥ 6 months
- Unprimed: previously unvaccinated children aged 6 months to <9 years

¹ Unprimed children who participate in the drug use investigation following the administration of both doses of *Fluarix Tetra*

² Unprimed children who participate in the drug use investigation following the administration of the first dose of *Fluarix Tetra*

³ Unprimed children who participate in the drug use investigation following the administration of the second dose of *Fluarix Tetra*

- 2nd dose would be given at least 4 weeks after the 1st dose.
- Signed informed consent as ICF/IAF obtained from the subject/subject's parent(s)/LAR(s).

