6.4. Outline of study procedures

Table 1 presents the list of drug use investigation procedures.

Table 1 List of study procedures

Type of contact	Enrolment **	Follow-up contact 21 days after vaccination **
Informed consent ¹	●	
Check inclusion/exclusion criteria	●	
Demographic data	●	
Medical history	●	
Vaccination history *	●	
Physical examination	●	
Pre-vaccination body temperature	●	
Record vaccination information	●	
Distribution of diary cards	○	
Record AEs within 21 days (Day 0 to Day 20) post-vaccination, by physician	●	●
Return of diary cards ^a		○
Diary card transcription by physician		●
Record concomitant medication/vaccination	●	●
Reporting of ADRs	●	●
Reporting of SAEs	●	●
Drug use investigation conclusion		●

● is used to indicate a study procedure that requires documentation in the individual CRF.

○ is used to indicate a study procedure that does not require documentation in the individual CRF.

¹Informed consent for participation into the drug use investigation can be taken after vaccination. The vaccination procedure is not part of the drug use investigation.

* Vaccination history is influenza vaccine history within the three previous seasons.

^a The subject/subject's parent(s)/LAR(s) will be instructed to return the completed diary card to the physician or phone or mail, to report any AEs/ADRs/SAEs during the 21 days (Day 0 to Day 20) using diary cards after *Fluarix Tetra* is administered.

^{**} Subjects who are pregnant and receive *Fluarix Tetra* or subjects who become pregnant within 21 days after receiving *Fluarix Tetra* should report to/notify GSK, if possible. Pregnancy outcome in vaccinated pregnant subjects will be followed-up at 6-8 weeks after delivery, if possible.

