10.5. Statistical methods

10.5.1. Analysis of demographics/baseline characteristics

Descriptive demographic characteristics (age, height, weight, gender, and ethnicity) of the study cohort will be tabulated.

In the descriptive summary, mean, standard deviation, median, minimum, and maximum will be computed for continuous variables such as age. Frequencies and percentages will be calculated for categorical variables such as gender.

The pre-existing medical history, vaccination history within the three previous seasons (yes/no), ***concomitant medication/vaccination at least once during the 21 days (Day 0 to Day 20) follow up period*** and record years will also be presented.

The distribution of subjects vaccinated among the drug use investigation centers by years will be tabulated.

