## 3. Analysis Sets

### 3.1 Safety Analysis Sets

The safety analysis set will include all subjects who receive Fluarix Tetra, participated in the drug use investigation and provide post vaccination safety data.

The cases below shall be excluded from safety analysis set in the following order:

- (1) Subjects who have consented prior to the contract
- (2) Subjects who have been administered prior to the contract\*
- (3) Subjects who didn't receive Fluarix Tetra within this study
- (4) Follow-up failure: Subjects for whom adverse event status (Adverse Events status is unknown or missing in CRF) could not be established
- (5) Subjects who violated inclusion/exclusion criteria (see section 2.3)
- (6) Subjects who were prescribed for other indications except indications in the local product document.

[Target Indication]

- Fluarix Tetra is indicated for active immunisation of adults and children from 6 months of age for the prevention of influenza disease caused by the influenza A virus subtypes and the influenza B virus types contained in the vaccine.

- (7) Subjects who violate the dosage

[Dosage]

- Children from 6 months and older receive 0.5 ml dose by intramuscular injection and is revaccination each year.
- For children aged < 9 years, who have not previously been vaccinated against influenza, a second dose should be given after an interval of at least 4 weeks.

	CONFIDENTIAL : THIS DOCUMENT AND INFORMATION CONTAINED HEREIN IS PROPRIETARY TO COMPANY AND IS NOT TO BE DISCLOSED WITHOUT THE WRITTEN PERMISSION OF COMPANY.	Last Update Date 10-SEP-2021
STATISTICAL ANALYSIS PLAN(V5.0)		

(8) Subjects of contraindications

[Contraindication]

- History of hypersensitivity to the active substances or to any of the excipients or to any component that may be present as traces such as eggs (ovalbumin, chicken proteins), formaldehyde, gentamicin sulphate and sodium deoxycholate
- Immunisation should be postponed in patients with febrile illness or acute infection.
- History of hypersensitivity reaction to Influenza vaccine
- History of Guillain-Barre syndrome or other nervous abnormalities to Influenza vaccine within 6 weeks post-vaccination

\* But subjects not administered the Fluarix Tetra this season shall be included from safety analysis set. In addition, subjects under age 9 years who participating in the drug use investigation with a second dose of Fluarix Tetra shall be included from safety analysis set.

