#### 6.3.1 Adverse Events by Subject Characteristics

For the AE(s) according to the subject characteristics\* such as gender and age in the safety assessment population:

- The number of subjects to whom AE occurred and the number of AEs will be calculated.
- The incidence proportion of AEs and its 95% confidence interval will be estimated and exploratory comparison between the group distributions will be performed using Chi-square test or Fisher's exact test. If there are two or more baseline characteristics that are statistically significant ( $p$ -value  $< 0.05$ ), they will be included in the logistic regression model to examine the effect of baseline characteristics on incidence of AEs. However, as considering the structure and characteristics of the collected data, the factors used for the actual analysis can be added or subtracted.

\* Incidence proportion for Route of concomitant vaccination and continuous variables not categorized  
 GlaxoSmithKline

	CONFIDENTIAL : THIS DOCUMENT AND INFORMATION CONTAINED HEREIN IS PROPRIETARY TO COMPANY AND IS NOT TO BE DISCLOSED WITHOUT THE WRITTEN PERMISSION OF COMPANY.	Last Update Date 10-SEP-2021
STATISTICAL ANALYSIS PLAN(V5.0)		

such as Height will be excluded from analysis.

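### The exploratory AE comparisons by influenza vaccination history and by pediatric group mix observation time with per-dose risk, because all children followed after two doses sit on one side of each comparison

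*SAP*

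**What the plan says.** **What is estimated.** SAP 6.3: "In the safety analysis set, the number of subjects to whom AE occurred and the number of AEs will be calculated". An incidence proportion with a 95% confidence interval follows. Protocol 10.5.2 admits to the safety analysis anyone vaccinated per the Korean PI with 21-day follow-up after at least one dose, however many doses were given. The endpoint in SAP 4.1 refers to 21 days after vaccination and does not say whether that means each dose or any dose.

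**Who has two windows.** Protocol section 3 sets a follow-up contact 21 days (Day 0 to Day 20) after each vaccination. Protocol 4.2 adds that the "2nd dose would be given at least 4 weeks after the 1st dose". Its table gives two follow-up contacts to one row only: unprimed children who take part for both doses. The definition is "Unprimed: previously unvaccinated children aged 6 months to <9 years". All other rows have one contact.

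**What is compared.** SAP 6.3.1 states that an "exploratory comparison between the group distributions will be performed using Chi-square test" or Fisher's exact test. It leaves out only route of concomitant vaccination and uncategorised continuous variables. The characteristics in SAP 6.2 include "Vaccination history (influenza vaccination, any non-influenza vaccination), Pre-vaccination body temperature, Dose of Fluarix Tetra administration(All subjects, Subjects under age 9 years", and also a pediatric group (3 to under 19 years, 3+ study group only). Protocol 10.5.1 summarises "vaccination history within the three previous seasons (yes/no" as a binary item, and the note to Table 1 in Protocol 6.4 confirms that "Vaccination history is influenza vaccine history within the three previous seasons".

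**The concern.** A subject observed for two 21-day windows has more opportunity to report an AE than a subject observed for one. If such subjects were spread evenly over the groups being compared, this would change the level of each proportion but not the contrast. The schedule does not spread them evenly: it puts all of them in one category of vaccination history and, in the 3+ group, in one category of the pediatric factor.

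A higher AE proportion in children without vaccination history, or in the pediatric group, could therefore arise partly or wholly from the second window. A reader of the report to the regulator could take it as greater susceptibility per dose. A significant result may also carry the factor into the logistic model of SAP 6.3.1, which has no term for number of windows. The tests are exploratory and do not affect conduct, so what is at stake is how the safety report is interpreted.

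**Working it through.** **1. The plan's own figure.** Protocol Table 4, n = 600, observed 10%: Clopper-Pearson for 60/600 gives 7.72-12.68%, matching the stated 7.7-12.7%. All eight rows reproduce to one decimal.

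**2. The windows do not overlap.** Each window is 21 days and doses are at least 28 days apart. Observation is therefore up to 21 days for one dose and up to 2 x 21 = 42 days for two.

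**3. Where the two-window children fall.**
- A child vaccinated in any of the three previous seasons is previously vaccinated, hence primed, and has one dose.
- A primed child given two doses off schedule would fall under "Subjects who violate the dosage" in SAP 3.1 and leave the safety set.
- So the history-yes group has 0% two-window subjects, and all two-window children are history-no.
- In the 3+ group they are aged 3 to under 9, so all are in the pediatric group.
- Both contrasted groups also hold one-window subjects, so the effect depends on the share with two windows.

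**4. Risk over two windows.** With per-dose risk p and within-child correlation ρ:

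q = 2p − [p² + ρp(1 − p)]

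The documents give neither p nor ρ. Assume p = 0.10.
- ρ = 0: q = 0.20 − 0.01 = 0.190
- ρ = 0.4: q = 0.20 − (0.01 + 0.036) = 0.154

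**5. Effect on the overall proportion.** With share w of the whole set having two windows, the overall proportion is (1 − w)p + wq. It is 10.5-10.9% at w = 10%, 11.4-12.3% at 25% and 12.7-14.5% at 50%.

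**6. Effect on the comparison.** History-yes subjects all have risk p. In the history-no group a share f has risk q and the rest p. Rejection rates of the two-sided pooled chi-square test at 0.05, by exact enumeration of the binomial counts, for ρ from 0.4 to 0:

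| f (assumed) | Risk in history-no | 300 yes v 300 no | 450 yes v 150 no |
|---|---|---|---|
| 0% | 10.0% | 5% | 5% |
| 10% | 10.5-10.9% | 6-7% | 6-7% |
| 25% | 11.4-12.3% | 8-14% | 8-13% |
| 50% | 12.7-14.5% | 18-39% | 16-33% |

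Per-dose risk is equal in all subjects here, so the excess over 5% comes only from the second window. At f = 50%, ρ = 0 and 300 v 300, the rate is 23% if p = 5% and 63% if p = 20%.

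**The case against.** The strongest reply is that nothing is wrong with the estimate. The objective is AE frequency when the vaccine is given according to the local PI, and for a previously unvaccinated young child that schedule is two doses. Pooling over number of doses is declared in Protocol 10.5.2. This stands. A reader might infer that the overall proportion is biased, or that rejections in the table are false positives. Neither follows: the proportion is a valid any-dose figure, and the rejections reflect a true any-dose difference. They mislead only if read as per-dose risk.

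A reader might also infer that the plan offers no AE incidence by dose. The documents do not support that. The dose-of-administration item in SAP 6.2 probably means dose number: the volume is fixed at 0.5 mL, dosage violators are excluded, and the separate display for under-9s matches the two-dose age limit. It is not excluded from SAP 6.3.1, so a by-dose AE table may already be planned there or in the mock TLFs, which are not shown. But its categories are undefined, and as a separate row it neither stratifies nor adjusts the history and pediatric comparisons. If it means one dose versus two, it carries the same 21 v 42 day difference. Nor does the SAP count only subjects: it counts AEs as well, and only the proportion is per subject.

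Finally, entry into the logistic model is not certain. SAP 6.3.1 requires at least two significant baseline characteristics and lets factors be added or removed.

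**Conclusion.** The concern holds as a matter of interpretation. The any-dose proportion should stay, but the vaccination-history and pediatric comparisons as planned cannot separate a longer observation period from a higher risk per dose.

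The direction and the placement of the two-window children follow from the documents. The size does not: per-dose risk, two-window share, within-child correlation and group split are all assumed. At a 10% share the test stays near its nominal level, and the overall proportion (10.5-10.9%) lies inside the protocol's own interval of 7.7-12.7%. At 25-50% the rejection rate is 8-39% for 300 v 300 at 10% risk.

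The issue matters mainly for vaccination history in the 6-35 months group, where every subject is within the two-dose age range and the pediatric factor does not apply. In the 3+ group it is likely small: adults are included, and the pediatric category runs to under 19 while two-window children are under 9. A reader might carry the higher rejection rates over to the pediatric comparison; nothing in the documents supports so large a two-window share there.

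**What to change.** 1. Define the categories of the dose-of-administration item in SAP 6.2. Unless that item or the mock TLFs already do so, tabulate AE, ADR and SAE incidence with exact confidence intervals for Day 0-20 after dose 1 and after dose 2, with the subjects followed after that dose as denominator.
2. Keep the per-subject proportion and label it as any dose, up to two 21-day windows. Report the number of subjects followed after first dose only, second dose only and both.
3. For vaccination history and pediatric group, and any logistic model that includes them, add a comparison restricted to the dose-1 window alongside the any-dose one. Show children followed only after dose 2 separately; taking each subject's first followed window instead would mix dose 1 and dose 2. Stratifying by number of followed windows is an alternative, but history-yes has no two-window subjects, so only the one-window stratum would inform that contrast.

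**Cost.** SAP wording and a few extra tables. The single-window comparison has fewer events, though second-window events stay in the dose-2 and any-dose tables. The dose-2 table is less precise: at an observed 10%, the exact 95% interval is 3.8-20.5% with 60 children, 5.7-16.0% with 150 and 6.8-14.0% with 300. Confirm first that the CRF, which is not in the documents, assigns each AE to a dose.

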#### 6.3.1 Adverse Events by Subject Characteristics

For the AE(s) according to the subject characteristics\* such as gender and age in the safety assessment population:

- The number of subjects to whom AE occurred and the number of AEs will be calculated.
- The incidence proportion of AEs and its 95% confidence interval will be estimated and exploratory comparison between the group distributions will be performed using Chi-square test or Fisher's exact test. If there are two or more baseline characteristics that are statistically significant ( $p$ -value  $< 0.05$ ), they will be included in the logistic regression model to examine the effect of baseline characteristics on incidence of AEs. However, as considering the structure and characteristics of the collected data, the factors used for the actual analysis can be added or subtracted.

\* Incidence proportion for Route of concomitant vaccination and continuous variables not categorized  
 GlaxoSmithKline

	CONFIDENTIAL : THIS DOCUMENT AND INFORMATION CONTAINED HEREIN IS PROPRIETARY TO COMPANY AND IS NOT TO BE DISCLOSED WITHOUT THE WRITTEN PERMISSION OF COMPANY.	Last Update Date 10-SEP-2021
STATISTICAL ANALYSIS PLAN(V5.0)		

such as Height will be excluded from analysis.

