6.3.4. Concomitant medication/vaccination

All concomitant medications/vaccinations according to local practice are allowed during the drug use investigation and administration of these should be documented in the CRF.

At each drug use investigation visit/contact, the physician should question the subject/subject's parent(s)/LAR(s) about any medication taken and vaccination received by the subject.

All concomitant medications/vaccinations, with the exception of vitamins and/or dietary supplements, are to be recorded in the CRF. This also applies to concomitant medication administered prophylactically in anticipation of reaction to the vaccination and any medication intended to treat an AE.

A prophylactic medication is a medication administered in the absence of any symptom and in anticipation of a reaction to the vaccination (e.g. an anti-pyretic is considered to be prophylactic when it is given in the absence of fever and any other symptom, to prevent fever from occurring [fever is defined as temperature ≥ 37.5 °C (99.5 °F) on oral/axillary/tympanic setting].

Similarly, concomitant medication administered for the treatment of an SAE, at any time, must be recorded on the CRF concomitant medication section and in the SAE report form, as applicable. Refer to Section 7.1.3 for the definition of a SAE.

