6.3.4.1. Time window for recording concomitant medication/vaccination in the CRF

All concomitant medications, with the exception of vitamins and/or dietary supplements, administered at any time during the period starting with the administration of *Fluarix Tetra* and ending 21 days (Day 0 to Day 20) after vaccination must be recorded in the CRF.

Any vaccine not foreseen in the drug use investigation protocol administered in the period beginning 21 days (Day -20 to Day 0) preceding the dose of *Fluarix Tetra* and ending 21 days (Day 0 to Day 20) after the dose of *Fluarix Tetra* must be recorded in the CRF.

Any investigational medication or vaccine administered throughout the drug use investigation (i.e. from 21 days before the first dose of the vaccine and 21 days after administration of the dose of the vaccine) must be recorded in the CRF.

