7.5. Treatment of adverse events

Treatment of any AE is at the sole discretion of the physician and according to current good medical practice. Any medication administered for the treatment of an AE should be recorded in the subject's CRF.

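### SAP 6.3.1 tests AE incidence by concomitant medication, a factor that includes drugs given to treat the AE, so this exploratory comparison is biased towards a positive association

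*SAP*

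**What the plan says.** SAP 6.3.1 (Adverse Events by Subject Characteristics) counts AEs within each subject characteristic, estimates the incidence proportion with a 95% confidence interval, and states that an "exploratory comparison between the group distributions will be performed using Chi-square test" or Fisher's exact test. SAP 6 sets the level at 0.05, two-sided.

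The characteristics are those of SAP 6.2. Its study-medication list contains "Concomitant medication, Concomitant vaccination, Route of concomitant vaccination". The baseline list is separate: "Gender, Age, Height, Weight, BMI, Ethnicity, General medical history/physical examination". The footnote to 6.3.1 removes only two kinds of item: "Incidence proportion for Route of concomitant vaccination and continuous variables not categorized". Route of concomitant vaccination stands under the same 6.2 heading as concomitant medication. Naming it as an exception implies that the other items under that heading are tested.

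SAP 6.2 does not define the concomitant medication variable, and the mock tables are not shown. The protocol gives its content:

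- Protocol 6.3.4, on what is recorded: "This also applies to concomitant medication administered prophylactically in anticipation of reaction to the vaccination and any medication intended to treat an AE".
- Protocol 6.3.4.1, on the window: medication "administered at any time during the period starting with the administration of" the vaccine, up to Day 20.
- Protocol 7.5: "Any medication administered for the treatment of an AE should be recorded in the subject's CRF".
- Protocol 10.5.1, on the summary: "concomitant medication/vaccination at least once during the 21 days (Day 0 to Day 20) follow up period".

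SAP 4.1 counts AEs over the same Day 0 to Day 20 period.

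**The concern.** A subject who has an AE, takes a drug for it and would not otherwise have taken any medication becomes a medication user because of the AE. Users are thereby enriched with AE cases and non-users depleted of them, even if no drug has any effect on AE risk. The test then tends to find that users have more AEs.

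A report to the regulator could therefore show a significant association between concomitant medication and AEs where none exists. The 6.3.1 test is not on the list in SAP 6 of analyses kept for the final report. Periodic reports would carry it without the SAP 6.3.3 tables, which are on that list.

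**Working it through.** The plan states no figure for this comparison, so there is none to reproduce.

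**Inputs from the documents.** Two-sided level 0.05 (SAP 6); chi-square or Fisher's exact test (SAP 6.3.1); 600 evaluable subjects per study group (Protocol 10.2, SAP 2.2).

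**Assumed inputs, because the documents give none.** AE risk *p*; background medication use *b*, unrelated to AE risk; share *t* of subjects with an AE who take a drug for it, independent of background use.

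**Odds ratio with no true effect.**

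- P(medication | AE) = *b* + (1 − *b*)*t*
- P(medication | no AE) = *b*
- OR = 1 + *t* / [*b*(1 − *t*)], which exceeds 1 for any *t* > 0

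**Worked cases at *p* = 0.10, *b* = 0.30.**

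- *t* = 0.10: P(medication | AE) = 0.30 + 0.70 × 0.10 = 0.37. AE risk in users = 0.037 / (0.037 + 0.270) = 12.1%; in non-users = 0.063 / (0.063 + 0.630) = 9.1%. OR = 1 + 0.10/0.27 = 1.37.
- *t* = 0.30: P(medication | AE) = 0.51. AE risk in users = 0.051 / (0.051 + 0.270) = 15.9%; in non-users = 0.049 / (0.049 + 0.630) = 7.2%. OR = 1 + 0.30/0.21 = 2.43.

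**Rejection rate at *n* = 600, *p* = 0.10, *b* = 0.30.** Exact enumeration of the 2×2 tables, uncorrected chi-square:

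| *t* | OR | Rejection |
|---|---|---|
| 0 | 1.00 | 5.0% |
| 0.05 | 1.18 | 9.3% |
| 0.10 | 1.37 | 21.0% |
| 0.20 | 1.83 | 59.2% |
| 0.30 | 2.43 | 89.3% |

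Fisher's test (4,000 simulated tables) gives 4.6%, 18.9% and 88.3% at *t* = 0, 0.10 and 0.30.

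**Range.** Over *p* = 5, 10, 20%, *b* = 20, 30, 40% and *t* = 10, 30%:

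- Lowest: OR 1.28 with rejection 10.5% (*p* = 5%, *b* = 40%, *t* = 10%).
- Highest: OR 3.14 with rejection 99.9% (*p* = 20%, *b* = 20%, *t* = 30%).

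**One periodic report.** With even enrolment of 720 over 6 years (assumed), a year holds 720/6 = 120 subjects. At *p* = 0.10 and *b* = 0.30, rejection at *t* = 0.10 and 0.30 is 9% and 33% by chi-square, and 6% and 26% by Fisher's test.

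**After the change.** If the factor is medication started before vaccination, a drug given for a post-vaccination AE cannot enter it, so *t* = 0. Under the same assumptions the OR is 1.00, and rejection at *n* = 600 is 4.8% to 5.0% over the same values of *p* and *b*.

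**Why not simply drop drugs marked as AE treatment.** Protocol 7.1.1 counts exacerbation of a pre-existing condition as an AE, so a drug already in use may be marked as treating one. Suppose a share *s* (assumed) of AE subjects on a prior drug lose it from the factor. Then P(medication | AE) = *b*(1 − *s*). With *b* = 0.30, *p* = 0.10 and *s* = 0.1, 0.2, 0.3, the OR is 0.86, 0.74 and 0.62, and rejection is 6.9%, 14.8% and 29.6%. The bias would run the other way.

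**The case against.** - **The tested variable is inferred.** SAP 6.2 leaves it undefined, and the derivation could in principle use the start-date or purpose item of SAP 6.3.3. This stands as a caveat. But nothing in 6.2 or 6.3.1 narrows the variable, and the protocol's recording rules and its summary definition point to any use during Day 0 to Day 20.
- **SAP 6.3.3 already separates the cases.** It tabulates AEs by treatment purpose and by start before vaccination. That helps a reader of the final report, but it does not change the factor tested in 6.3.1, and it is absent from periodic reports.
- **The periodic figures depend on the test and the report size.** SAP 6.3.1 gives no rule for choosing between the two tests. At 120 subjects the expected counts are small enough that Fisher's test would often be used, and at 10% treated its 6% is little above nominal. If the early reports are twice-yearly with about 60 subjects, rejection is about 5% and 15% at 10% and 30% treated, using Fisher's test when an expected count falls below 5. This stands. The distortion is clearest in the pooled final analysis.
- **The bias may spread to the logistic model.** That model selects baseline characteristics, and 6.2 lists concomitant medication under another heading. SAP 6.3.1 also lets factors be added. The text does not settle the matter, so no claim about the model is made here.
- **An odds ratio of 1.00 after the change is by construction.** It assumes prior medication is unrelated to AE risk. Prior users may truly differ, for example through pre-existing conditions. Such a difference would be a real association at baseline, not one produced by treating the AE.

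**Conclusion.** The concern holds and is minor. As written, the 6.3.1 comparison by concomitant medication uses a factor partly caused by the outcome. The upward direction follows from the protocol's recording rules and needs only that some subjects with an AE take a drug for it who would not otherwise have been users. The size rests wholly on assumed rates: false-positive rates at 600 subjects run from 10.5% to 99.9% over the range shown, and 9.3% in the milder case of 5% treated.

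The comparison is exploratory. The overall AE proportions and their exact confidence intervals, which serve the objective in Protocol 2, are unaffected, and Protocol 10.4.2 states that periodic results do not change conduct.

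**What to change.** Add one sentence to SAP 6.3.1 defining the tested factor as medication started before vaccination (yes/no), from the start-date item that SAP 6.3.3 already uses. It should specify:

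- Vaccination means the subject's first dose in the investigation. Otherwise, in children followed after two doses, a drug given for an AE after dose 1 would count as started before dose 2.
- A drug first taken on Day 0 counts as no.
- No further exclusion by AE-treatment purpose, since that would condition on the outcome.
- The same definition applies if the factor is ever added to the logistic model.
- Use of any medication stays as a descriptive frequency, without a test.

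The cost is that sentence and one derived variable; no new data are needed. Drugs first taken on or after the day of vaccination, including prophylactic or unrelated ones, leave the tested factor and appear only in the descriptive tables.
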